4.5.16 Optional Samples for Research Biosample Repository

4.5.16.1 Overview of the Research Biosample Repository

The Research Biosample Repository (RBR) is a centrally administered group of facilities used for the long-term storage of human biological specimens, including body fluids, solid tissues, and derivatives thereof (e.g., DNA, RNA, proteins, peptides). The collection, storage, and analysis of RBR samples will facilitate the rational design of new pharmaceutical agents and the development of diagnostic tests, which may allow for [REDACTED] drug therapy for patients in the future.

Samples for the RBR will be collected from patients who give specific consent to participate in this optional research. RBR samples will be analyzed to achieve one or more of the following objectives:

- To study the association of biomarkers with efficacy or disease progression
- To identify safety biomarkers that are associated with susceptibility to developing adverse events or can lead to improved adverse event monitoring or investigation
- To increase knowledge and understanding of disease biology and drug safety
- To study drug response, including drug effects and the processes of drug absorption and disposition
- To develop biomarker or diagnostic assays and establish the performance characteristics of these assays

4.5.16.2 Approval by the Institutional Review Board or Ethics Committee

Collection, storage, and analysis of RBR samples is contingent upon the review and approval of the exploratory research and the RBR portion of the Informed Consent Form by each site's IRB/EC and, if applicable, an appropriate regulatory body. If a site has not been granted approval for RBR sampling, this section of the protocol (Section [4.5.16](#)) will not be applicable at that site.

4.5.16.3 Sample Collection

The following samples will be stored in the RBR and used for research purposes, including, but not limited to, research on biomarkers related to BFKB8488A, diseases, or drug safety:

- Leftover blood, serum, plasma, urine, stool, and liver tissue samples (with the exception of remaining archival tissue blocks, which will be returned to sites) and any derivatives thereof (e.g., DNA, RNA, proteins, peptides)

The above samples may be sent to one or more laboratories for analysis of germline or somatic variants via WGS, WES, or other genomic analysis methods. Genomics is increasingly informing researcher's understanding of disease pathobiology. WGS and WES provide a comprehensive characterization of the genome and exome, respectively, and, along with clinical data collected in this study, may increase the opportunity for developing new therapeutic approaches or new methods for monitoring efficacy and safety or predicting which patients are more likely to respond to a drug or develop adverse events.

Data generated from RBR samples will be analyzed in the context of this study but may also be explored in aggregate with data from other studies. The availability of a larger dataset will assist in identification and characterization of important biomarkers and pathways to support future drug development.

For sampling procedures, storage conditions, and shipment instructions, see the laboratory manual.

RBR samples are to be stored until they are no longer needed or until they are exhausted. However, the RBR storage period will be in accordance with the IRB/EC-approved Informed Consent Form and applicable laws (e.g., health authority requirements).

4.5.16.4 Confidentiality

RBR samples and associated data will be labeled with a unique patient identification number.

Patient medical information associated with RBR samples is confidential and may be disclosed to third parties only as permitted by the Informed Consent Form (or separate authorization for use and disclosure of personal health information) signed by the patient, unless permitted or required by law.

Given the complexity and exploratory nature of the analyses of RBR samples, data derived from these analyses will generally not be provided to study investigators or patients unless required by law. The aggregate results of any conducted research will be available in accordance with the effective Sponsor policy on study data publication.

Data generated from RBR samples must be available for inspection upon request by representatives of national and local health authorities, and Sponsor monitors, representatives, and collaborators, as appropriate.

Any inventions and resulting patents, improvements, and/or know-how originating from the use of the RBR data will become and remain the exclusive and unburdened property of the Sponsor, except where agreed otherwise.

4.5.16.5 Consent to Participate in the Research Biosample Repository

The Informed Consent Form will contain a separate section that addresses participation in the RBR. The investigator or authorized designee will explain to each patient the objectives, methods, and potential hazards of participation in the RBR. Patients will be told that they are free to refuse to participate and may withdraw their consent at any time and for any reason during the storage period. A separate, specific signature will be required to document a patient's agreement to provide optional RBR samples. Patients who decline to participate will not provide a separate signature.

The investigator should document whether or not the patient has given consent to participate and (if applicable) the date(s) of consent, by completing the RBR Research Sample Informed Consent eCRF.

In the event of an RBR participant's death or loss of competence, the participant's samples and data will continue to be used as part of the RBR research.

4.5.16.6 Withdrawal from the Research Biosample Repository

Patients who give consent to provide RBR samples have the right to withdraw their consent at any time for any reason. After withdrawal of consent, any remaining samples will be destroyed or will no longer be linked to the patient. However, if RBR samples have been tested prior to withdrawal of consent, results from those tests will remain as part of the overall research data. If a patient wishes to withdraw consent to the testing of his or her RBR samples during the study, the investigator must inform the Medical Monitor in writing of the patient's wishes through use of the appropriate RBR Subject Withdrawal Form and must enter the date of withdrawal on the RBR Research Sample Withdrawal of Informed Consent eCRF. If a patient wishes to withdraw consent to the testing of his or her RBR samples after closure of the site, the investigator must inform the Sponsor by emailing the study number and patient number to the following email address:

[contact]

A patient's withdrawal from this study does not, by itself, constitute withdrawal of consent for testing of RBR samples. Likewise, a patient's withdrawal of consent for testing of RBR samples does not constitute withdrawal from this study.

4.5.16.7 Monitoring and Oversight

RBR samples will be tracked in a manner consistent with Good Clinical Practice by a quality-controlled, auditable, and appropriately validated laboratory information management system, to ensure compliance with data confidentiality as well as adherence to authorized use of samples as specified in this protocol and in the Informed Consent Form. Sponsor monitors and auditors will have direct access to appropriate parts of records relating to patient participation in the RBR for the purposes of verifying the data provided to the Sponsor. The site will permit monitoring, audits, IRB/EC review, and health authority inspections by providing direct access to source data and documents related to the RBR samples.

4.6 TREATMENT, PATIENT, STUDY, AND SITE DISCONTINUATION

4.6.1 Study Treatment Discontinuation

Patients must permanently discontinue study treatment if they experience any of the following:

- Any medical condition that the investigator or Sponsor determines may jeopardize the patient's safety if he or she continues to receive study treatment
- Investigator or Sponsor determination that treatment discontinuation is in the best interest of the patient
- Pregnancy
- Any adverse event CTCAE Grade 4 or higher, regardless of attribution to study drug
- Positively detected suicidal ideation type 4 or 5 or suicidal behavior
- 24-hour urinary cortisol $>1.5 \times$ ULN and $>2 \times$ baseline, if confirmed on follow up visit within 2 weeks.
- If any signs or symptoms of hyper- or hypothyroidism that accompany changes in thyroid function tests (TSH or free T4) that are confirmed by repeat testing.
- Abnormal IGF-1 that is confirmed by repeat testing.
- Nontraumatic bone fracture

The primary reason for study treatment discontinuation should be documented on the appropriate eCRF. Patients who discontinue study treatment prematurely will not be replaced. Patients who discontinue treatment prior to study treatment completion will participate in the end-of-treatment visit at the time of early discontinuation and will enter a follow-up period for a total of 6 weeks.

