2.1 EFFICACY OBJECTIVES

2.1.1 Primary Efficacy Objective

The primary efficacy objective for this study is to evaluate the efficacy of BFKB8488A compared with placebo on the basis of the following endpoint:

- Proportion of patients with resolution of NASH on overall histopathological reading, without worsening of fibrosis at Week 52. Resolution of NASH is defined as a NAS of 0–1 for inflammation, 0 for ballooning, and any value for steatosis as determined by a central reader. Worsening of fibrosis is defined as any increase in NASH Clinical Research Network (CRN) fibrosis stage as determined by a central reader.

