2.1.2 Secondary Efficacy Objective

The secondary efficacy objective for this study is to evaluate the efficacy of BFKB8488A compared with placebo on the basis of the following endpoints:

- Change from baseline in hepatic fat fraction as assessed by magnetic resonance imaging–derived proton density fat fraction (MRI-PDFF) at Week 52
- Proportion of patients with improvement in liver histology from baseline, defined as ≥ 2 points reduction in NAS with at least a 1-point reduction in either lobular inflammation or hepatocellular ballooning AND no worsening of fibrosis stage as determined by a central reader at Week 52
- Proportion of patients with improvement in liver fibrosis greater than or equal to one stage (as defined by the NASH CRN fibrosis stage) and no worsening of steatohepatitis (defined as no increase in NAS for ballooning, inflammation, or steatosis), determined by a central reader at Week 52

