To ensure an accurate baseline, two measurements will be taken for AST and ALT for all patients, first during the initial screening and then during the main screening approximately 4 weeks later (at least 2 weeks apart). A Fibroscan® assessment will also be performed during the initial screening to establish a baseline for all patients; a

The initial screening and the main screening may overlap; assessments for the initial screening and main screening may be done at the same time.

If a patient does not meet all eligibility criteria within the screening period (*with up to 2 week allowance for delays in laboratory (including biopsy) and MRI reporting or unforeseen scheduling issues*), re-screening is permitted once, at the investigator's discretion. Patients are not required to re-sign the consent form if they are re-screened within 8 weeks after previously signing the consent form. The investigator will record reasons for screen failure in the screening log (see Section 4.5.1 and Section 8.1). Re-screening patients must meet all eligibility criteria. Labs and tests performed within the last 8 weeks prior to re-screening do not need to be repeated (except pregnancy tests, insulin, lipids, AST/ALT, and HbA_{1c}, unless approved by the Medical Monitor).

The biopsy

[figure not shown]
will not need to be repeated if an archival sample is available from a biopsy performed no more than 6 months before randomization.

In order to establish a stable baseline for the study, all patients must be compliant with current medication and avoid any atypical physical activity for the week immediately prior to randomization. In addition, patients will be instructed to adhere to a diet consistent with guidelines for weight maintenance and a healthy lifestyle. These instructions should be given to the patients as early as possible during the screening period.

During the treatment period, patients will receive Q2W SC injections of BFKB8488A or placebo. Patients will receive a total of 26 (Q2W) doses.

Patients who complete the treatment period or discontinue treatment early will enter a follow-up period for a total of 6 weeks. Patients will be asked to come in for follow-up and evaluation as described in the schedule of activities.

Figure 1 Study Schema

Wk=Week

BFKB8488A—Genentech, Inc.
37/Protocol GC41033, Version 6

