4.6.2 Patient Discontinuation from the Study

Patients have the right to voluntarily withdraw from the study at any time for any reason. In addition, the investigator has the right to withdraw a patient from the study at any time.

Reasons for patient discontinuation from the study may include, but are not limited to, the following:

- Patient withdrawal of consent
- Study termination or site closure
- Adverse event
- Loss to follow-up
- Patient non-compliance, defined as failure to comply with protocol requirements as determined by the investigator or Sponsor

Every effort should be made to obtain a reason for patient discontinuation from the study. The primary reason for discontinuation from the study should be documented on the appropriate eCRF. Patients in the fixed dose cohorts who withdraw from the study will not be replaced unless the IMC elects to change the dose, see Section 3.1.2.

Patients in the [REDACTED] may be replaced as determined by the IMC, see Section 3.1.2. Patients who discontinue from the study will participate in the end-of-treatment visit at the time of discontinuation.

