6. STATISTICAL CONSIDERATIONS AND ANALYSIS PLAN

The primary efficacy objective for this study is to evaluate the efficacy of BFKB8488A compared with placebo on the basis of the proportion of patients with resolution of NASH and no worsening of fibrosis. The primary and secondary efficacy analyses will be based on a modified intent-to-treat (mITT) approach. All patients who received at least one dose of study drug will be included in the mITT population, with patients grouped according to the treatment assigned at randomization. Analyses will be based on the final biopsy at Week 52 or MRI-PDFF measured over the course of the study.

The final analysis of data from the study will be performed when all patients have either: (i) completed the Week 52 visit and associated liver biopsy or (ii) withdrawn from the study prior to Week 52. The data analysis plan (DAP) will be specified prior to unblinding.

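### Do patients who stop study drug before about Week 46 need follow-up to Week 52 so that the primary endpoint can be observed?

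*Combined protocol and SAP*

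**What the plan says.** Sections 3.1 and 4.6.1 set the follow-up. Section 3.1 states: "Patients who complete the treatment period or discontinue treatment early will enter a follow-up period for a total of 6 weeks". Section 4.6.1 adds that a patient who stops before completing treatment "will participate in the end-of-treatment visit at the time of early discontinuation and will enter a follow-up period for a total of 6 weeks". For a patient who leaves the study altogether, Section 4.6.2 says: "Patients who discontinue from the study will participate in the end-of-treatment visit at the time of discontinuation".

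The endpoints are fixed in time. Section 2.1.1 defines the primary endpoint as "Proportion of patients with resolution of NASH on overall histopathological reading, without worsening of fibrosis at Week 52", and the NAS endpoint in Section 2.1.2 ends "AND no worsening of fibrosis stage as determined by a central reader at Week 52".

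Section 6 defines the analysis: "All patients who received at least one dose of study drug will be included in the mITT population", and "Analyses will be based on the final biopsy at Week 52" or on MRI-PDFF measured during the study. The final analysis waits until every patient has "completed the Week 52 visit and associated liver biopsy or (ii) withdrawn from the study prior to Week 52".

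The assessment sections use a different time label. Sections 4.5.9, 4.5.10.1 and 4.5.10.2 place the second biopsy and its scoring at end of treatment, and Section 4.5.12 makes that sample conditional on clinical feasibility. Section 6.4.1 leaves missing-data handling to the DAP. The schedule of activities is redacted.

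**The concern.** Read together, these sections seem to leave a hole. Early stoppers stay in the modified intent-to-treat set, but nothing readable brings them back at Week 52. A biopsy may exist from the early end-of-treatment visit, yet one section speaks of a biopsy at Week 52 and others of a biopsy at end of treatment, and the text does not say whether the early one counts. The trigger for the final analysis also does not name a patient who stopped drug and then completed the 6-week follow-up.

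The stake would be the estimated effect of each dose. Section 4.6.1 requires stopping for confirmed changes in urinary cortisol or IGF-1, and for symptomatic thyroid changes. These concern the hormonal axis that Section 5.1.1.4 monitors as a possible drug effect. If stopping differed by arm, the result for each dose would depend in part on how missing Week 52 results are filled, in a trial meant to compare doses. A DAP can classify or impute, but it cannot create an observation that was never made.

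**Working it through.** **Inputs.** The Synopsis (Determination of Sample Size) gives a 15% placebo rate, a 30-point increase (so 45% on drug), a two-sided 0.05 test, 10% lost to follow-up, and arms of 20 (50 mg), 60 (75 mg), 60 (100 mg) and 40 (placebo). Stated power for the fixed cohort alone is 87% for 75 or 100 mg and 66% for 50 mg.

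**Timing.** Follow-up ends at the stopping week + 6. It reaches Week 52 only if the stop is at Week 52 − 6 = 46 or later. A stop at Week 26 ends at Week 32. The further follow-up needed to reach Week 52 is 46 minus the stopping week: 36 weeks for a stop at Week 10, 20 for Week 26, 6 for Week 40.

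**Formula.** Power = Φ[(|p₂ − p₁| − 1.96·SE₀)/SE₁], where SE₀ uses the pooled rate and SE₁ the separate rates.

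**Plan's figures first.** With 10% removed from each arm and 15% v 45%:
- 36 v 54: 87.0% (stated 87%)
- 36 v 18: 66.2% (stated 66%)

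Both reproduce.

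**Rules compared at 10%.** This is 2 + 6 + 6 + 4 = 18 of 180 patients, all taken to be early stoppers. Power is for 75 or 100 mg v the fixed-cohort placebo arm. The range in the last row assumes that drug-arm stoppers respond at anything from 15% to 45% and placebo stoppers at 15%.

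| Rule | Rates, placebo v drug | Difference | Power |
|---|---|---|---|
| Removed | 15% v 45% | 30 points | 87.0% (36 v 54) |
| Counted as non-responders | 0.9 × 15% = 13.5% v 0.9 × 45% = 40.5% | 27 points | 85.2% (40 v 60) |
| Early biopsy used, or Week 52 biopsy off drug | 15% v 0.9 × 45% + 0.1 × (15% to 45%) = 42% to 45% | 27 to 30 points | 84.0% to 90.5% (40 v 60) |

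For 50 mg, removal gives 66.2% and non-responder counting 64.6%.

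**Pooled placebo.** The primary comparison uses pooled placebo, whose size is redacted. Assuming 50 to 80 patients, power for 75 or 100 mg is 91.2% to 96.2% with removal and 89.8% to 95.4% with non-responder counting, a fall of 1.4 to 0.8 points.

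**Unequal stopping (assumed; the documents give no rates).** The placebo arm has 10% stopping throughout.
- 20% on drug: removal keeps 30 points. Non-responder counting gives 0.8 × 45% − 13.5% = 22.5. Retention gives 0.8 × 45% + 0.2 × (15% to 45%) − 15% = 24 to 30.
- 30% on drug: removal keeps 30 points. Non-responder counting gives 0.7 × 45% − 13.5% = 18.0. Retention gives 0.7 × 45% + 0.3 × (15% to 45%) − 15% = 21 to 30.

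**The case for a change.** The best case for acting is that the three factual parts are right. A stop before about Week 46 does end follow-up before Week 52, no readable text provides a Week 52 assessment for such a patient, and none says how an early biopsy is classified. Under unequal stopping the rules diverge: at an assumed 20% on drug and 10% on placebo, fixed-cohort power for 75 or 100 mg is 85.4% with removal and 71.8% with non-responder counting. Only follow-up to Week 52 gives a result at the time the endpoint names, and that must be arranged while patients are still in the study.

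The factual parts stand. The step to an amendment does not.

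- The absence falls where the text is redacted. The schedule of activities would show an early-termination biopsy or a retained Week 52 visit, so the readable text cannot establish that neither exists.
- No source supports unequal stopping of that size. Section 3.3.1 describes the three fixed doses as tolerated in Phase Ib.
- Staying to Week 52 has a price. A patient who stays gives up the on-drug biopsy at stopping, may be lost during up to 36 further weeks (for a Week 10 stop), and may start therapies that Section 4.4.2 no longer prohibits after stopping. The off-drug biopsy answers a different question from the end-of-treatment one; it is not simply a better measurement of the same thing.
- The MRI endpoint is less exposed. Section 6 draws on MRI-PDFF over the course of the study and Section 6.10.1 shows a Week 16 scan, so earlier data will exist for many early stoppers.

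**Conclusion.** The concern does not call for a change. It combines a gap that analysts fill sensibly with a fair trade-off.

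The gap is how an early or absent biopsy is classified. Section 6.4.1 already assigns missing-data handling to the DAP, Sections 6 and 6.4 fix the DAP before unblinding, and Section 6.4 foresees sensitivity analyses in other populations. The sample size allows for 10% loss. A patient who stopped drug and finished follow-up early fits most naturally into the second category of the final-analysis trigger, as someone no longer in the study at Week 52. A statistician writing the DAP would settle both points as a matter of routine.

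The trade-off is whether to follow willing patients off drug to Week 52. At the plan's 10% loss this gives the same 27 to 30 points as using early biopsies, and its power of 84.0% to 90.5% may fall below the 85.2% from non-responder counting. The sponsor may weigh it as an option, but its absence is not an error.

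The size at stake is at most 3 points in the expected difference and about 2 points of fixed-cohort power. This assumes 10% stopping in every arm and drug-arm stoppers responding at 15% to 45%. Markedly unequal stopping would widen the spread, but the documents give no rates to support it. The redacted schedule could settle the question either way.

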4.6.2 Patient Discontinuation from the Study

Patients have the right to voluntarily withdraw from the study at any time for any reason. In addition, the investigator has the right to withdraw a patient from the study at any time.

Reasons for patient discontinuation from the study may include, but are not limited to, the following:

- Patient withdrawal of consent
- Study termination or site closure
- Adverse event
- Loss to follow-up
- Patient non-compliance, defined as failure to comply with protocol requirements as determined by the investigator or Sponsor

Every effort should be made to obtain a reason for patient discontinuation from the study. The primary reason for discontinuation from the study should be documented on the appropriate eCRF. Patients in the fixed dose cohorts who withdraw from the study will not be replaced unless the IMC elects to change the dose, see Section 3.1.2.

Patients in the [REDACTED] may be replaced as determined by the IMC, see Section 3.1.2. Patients who discontinue from the study will participate in the end-of-treatment visit at the time of discontinuation.

